9.2. Safety objectives

Secondary objectives are to:

- compare the change in potassium levels over the trial between S2C and placebo groups
- compare the change in BP over the trial between S2C and placebo groups
- compare the proportion experiencing an adverse event during the trial between S2C and placebo groups
- compare the proportion experiencing high levels of potassium at any point during the trial between S2C and placebo groups
- compare the proportion experiencing low levels of potassium at any point during the trial between S2C and placebo groups
- compare the proportion experiencing sudden large decline in eGFR during the trial between S2C and placebo groups
- compare the change in eGFR over the trial between S2C and placebo groups.

10. STUDY ENDPOINTS

10.1. Primary endpoint

The primary endpoint is the achievement of reaching maximum dose of irbesartan at the end of the trial (12 weeks).

10.2. Safety endpoints

Safety endpoints are:

- change in potassium from baseline to the time-point of each trial visit (1 week, 2 weeks, 4 weeks, 6 weeks, 8 weeks, and 12 weeks)
- change in office BP (systolic and diastolic) from baseline to the end of the trial (12 weeks)
- experiencing an adverse event during the trial (to 12 weeks)
- experiencing potassium levels higher than 6 mmol/L, and higher than 6.5 mmol/L at any point during the trial (to 12 weeks)
- experiencing potassium levels lower than 3.5 mmol/L at any point during the trial (to 12 weeks)
- experiencing a reduction in eGFR more than 30% from the previous visit test
- change in eGFR from baseline to the end of the trial (12 weeks).

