#### 11.3.2 Safety Endpoints

- Change in potassium from baseline at each time point
- Change in the BP at the end of the study from baseline
- Frequency of adverse events
- Proportion of patients who have a K of >6, or >6.5 at any time during the study
- Proportion of patients who have a K of <3.5 at any time during the study
- Proportion of patients whose GFR falls by >30% from the previous test
- Change in (eGFR) renal function at the end of study from baseline

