### 13.8.3 Trial assessments

#### Screening visit

- a. Informed consent
- b. Inclusion/Exclusion criteria
- c. Demographic data
- d. Concomitant Medication
- e. Physical examination
- f. Medical history
- g. ECG with QTc (f) measured
- h. Vital signs (weight/height/BP/pulse)
- i. Laboratory investigations: U+E
- j. Pregnancy test for women of childbearing potential
- k. Stop all antihypertensive medications (unless judged by PI as fulfilling other purpose eg: beta blockers may continue in patients with angina/arrhythmia or as judged by PI as a risk to health to stop all antihypertensives.)

Rescreening: If patient does not meet the inclusion/exclusion criteria patients, but PI feels there is a likelihood of subsequently meeting criteria then the patient may be rescreened (up to a maximum of 3 times)

Within 7-14 days of screening visit

#### Randomisation visit 1

- a. Concomitant Medication
- b. ECG with QTc (f) measured
- c. Confirmation of meeting Inclusion and no Exclusion criteria
- d. Physical examination
- e. Vital signs (weight/BP/Pulse)
- f. Urine ACR
- g. Lab bloods: U+E (including bicarbonate) , FBC, NT pro BNP
- h. Point of care potassium (optional)
- i. Adverse event assessment (AE and SAE)
- j. Randomisation
- k. Study drug dispense and irbesartan dose chosen as per K value\*\*
- l. Patient shown how to take IMP and given first dose in clinic.

Visit 2,3,4,5,6: see protocolised

- a. Concomitant Medication:
- b. IMP accountability\*
- c. Physical examination
- d. Vital signs (weight/BP/Pulse)
- e. ECG with QTc(f) measured
- f. Lab bloods: U+E (including bicarbonate)
- g. Point of care potassium (optional)
- h. Adverse event assessment (AE and SAE)
- i. Up titration assessment using BP/K\*\*/GFR : see protocol figure 13.8.2
- j. Dispense IMP: visit 4 +6 only. At visits 2,3 and 5 unused IMP and nIMP are returned to the patient after accountability.

## Visit 7

- a. Concomitant Medication review
- b. IMP and RASI accountability\*
- c. Physical examination
- d. Vital signs (weight/BP/Pulse)
- e. ECG with QTc (f) measured
- f. Lab bloods: FBC, U+E (including bicarbonate), Pro NT BNP
- g. Point of care potassium (optional)
- h. uACR
- i. Adverse event assessment (AE and SAE)
- j. IMP stopped
- k. Irbesartan stopped and patient returned to their original dose of ACE/ARB

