## 17 Pharmacovigilance

### 17.1 General Definitions

Term	Definition
Adverse Event (AE)	Any untoward medical occurrence in a participant to whom a medicinal product has been administered, including occurrences which are not necessarily caused by or related to that product.
Adverse Event of Special interest (AESI)	An adverse event of special interest (serious or non-serious) is one of scientific and medical concern specific to the sponsor's product or programme, for which ongoing monitoring and rapid communication by the investigator to the sponsor could be appropriate. Such an event might require further investigation in order to characterise and understand it. Depending on the nature of the event, rapid communication by the trial sponsor to other parties (e.g., regulators) might also be warranted.
Adverse Reaction (AR)	An untoward and unintended response in a participant to an investigational medicinal product which is related to any dose administered to that participant. The phrase "response to an investigational medicinal product" means that a causal relationship between a trial medication and an AE is at least a reasonable possibility, i.e. the relationship cannot be ruled out. All cases judged by either the reporting medically qualified professional or the Sponsor as having a reasonable suspected causal relationship to the trial medication qualify as adverse reactions.
Serious Adverse Event (SAE)	A serious adverse event is any untoward medical occurrence that: 
 
• Results in death.
 
• Is life-threatening.
 
• Requires inpatient hospitalisation or prolongation of existing hospitalisation
 
• Results in persistent or significant disability/incapacity.
 
• Consists of a congenital anomaly or birth defect.
 
 SAEs will be collected from the time the patient signs the consent form until their last study visit. Other 'important medical events' may also be considered serious if they jeopardise the participant or require an intervention to prevent one of the above consequences. NOTE: The term "life-threatening" in the definition of "serious" refers to an event in which the participant was at risk of death at the time of the event; it does not refer to an event which hypothetically might have caused death if it were more severe.

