8.2. Safety objectives

	Safety Objectives	Secondary Endpoints	Outcome measures
2.1	To compare the change in potassium levels over the trial between SZC and placebo groups.	Change in potassium from baseline to the time-point of each trial visit (1 week, 2 weeks, 4 weeks, 6 weeks, 8 weeks, and 12 weeks).	Mean difference in change in potassium from baseline to each trial visit between SZC and placebo groups.
2.2	To compare the change in BP over the trial between SZC and placebo groups.	Change in office BP (Systolic and diastolic) from baseline to the end of the trial (12 weeks).	Mean difference in change in BP from baseline to the end of the trial (12 weeks) between SZC and placebo groups.

2.3	To compare the proportion experiencing an adverse event during the trial between S2C and placebo groups.	Experiencing adverse events during the trial (to 12 weeks).	The difference in proportion of patients experiencing a adverse events between baseline and the end of the study (12 weeks) between S2C and placebo groups.
2.4	To compare the proportion experiencing high levels of potassium at any point during the trial between S2C and placebo groups.	Experiencing potassium levels higher than 6 mmol/L, and higher than 6.5 mmol/L at any point during the trial (to 12 weeks).	Difference in proportion of patients experiencing potassium levels higher than 6 mmol/L, and higher than 6.5 mmol/L at any point during the trial (to 12 weeks) between S2C and placebo groups.
2.5	To compare the proportion experiencing low levels of potassium at any point during the trial between S2C and placebo groups.	Experiencing potassium levels lower than 3.5 mmol/L at any point during the trial (to 12 weeks).	Difference in proportion of patients experiencing potassium levels lower than 3.5 mmol/L at any point during the trial (to 12 weeks) between S2C and placebo groups.
2.6	To compare the proportion experiencing sudden large decline in eGFR during the trial between S2C and placebo groups.	Experiencing a reduction in eGFR more than 30% from the previous visit test.	Difference in proportion of patients experiencing reduction in eGFR more than 30% from the previous visit test between S2C and placebo groups.
2.7	To compare the change in eGFR over the trial between S2C and placebo groups.	Change in eGFR from baseline to the end of the trial (12 weeks).	Mean difference in change in eGFR from baseline to the end of the trial (12 weeks) between S2C and placebo groups.

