11. ASSESSMENT OF OBJECTIVES

Upon successful screening and meeting all eligibility criteria for inclusion into the trial, as specified in the protocol, consenting patients will be randomised to either receive Szc therapy or placebo. Patients will receive trial treatment in accordance with the protocolised management of irbesartan and Szc/placebo, as described in Figure 2.

[figure not shown]
After screening and baseline, patients will be assessed at 1 week, 2 weeks, 4 weeks, 6 weeks, 8 weeks and 12 weeks (end of the trial), as well as a further follow-up assessment at 14 weeks post baseline. The assessment schedule is shown in the Table 1.

Table 1: Schedule of assessment

Schedule of visits	Screening	Visit 1	Visit 2	Visit 3	Visit 4	Visit 5	Visit 6	Visit 7	Follow-up visit	Unscheduled	Early termination visit
Day/Month	Day -14 to -7	Day 0	Day 7 (+/- 2)	Day 14 (+/- 4)	Day 28 (+/- 4)	Day 42 (+/- 4)	Day 56 (+/- 4)	Day 84 (+/- 4)	Day 98 (+/- 4)		
Informed Consent	X										
Eligibility criteria	X	X									
Demographic data	X										
Medical history	X										
Pregnancy test if WOCBP	X										
Concomitant medication	X	X	X	X	X	X	X	X	X	if needed	X
Randomisation		X									
Stop background antihypertensives	X										
First IMP dose at site		X									
Drug accountability (IRB and SZC)			X	X	X	X	X	X		If needed	
IMP and NIMP drug dispense		X			X		X			If needed	
Physical examination	X	X	X	X	X	X	X	X	X	If needed	X
Vital signs	X	X	X	X	X	X	X	X	X	If needed	X
FBC		X						X		If needed	
U+E	X	X	X	X	X	X	X	X	X	If needed	X
Pro NT BNP		X						X			
Optional POC potassium		X	X	X	X	X	X	X			
ECG	X	X	X	X	X	X	X	X	X	If needed	X
Urine collection (uACR)		X						X		If needed	

AE assessment		X	X	X	X	X	X	X	X	X	X
Uptitration of RASI			X	X	X	X	X			If needed	
RASI dose back to baseline								X			X

Figure 2: Protocolised management of irbesartan and SZC/placebo

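### The SAP ends its potassium-excursion and adverse-event counts at week 12, although the protocol sets no such limit and collects both at Day 98

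*SAP*

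**What the plan says.** **Protocol.** The high-potassium endpoint in 11.3.2 is "Proportion of patients who have a K of >6, or >6.5 at any time during the study". The low-potassium endpoint (<3.5 mmol/L) has the same open window, and 11.5 and 19.3 repeat both. The adverse-event endpoint in 11.3.2 is a frequency with no cut-off. Section 17.1 adds: "SAEs will be collected from the time the patient signs the consent form until their last study visit". At Visit 7 (Day 84) the IMP is stopped and, in 13.8.3, "Irbesartan stopped and patient returned to their original dose of ACE/ARB". Visit 8 (Day 98, section 13.8.4) takes U+E, an ECG and an adverse-event assessment.

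**SAP.** Section 10.2 limits high potassium to "experiencing potassium levels higher than 6 mmol/L, and higher than 6.5 mmol/L at any point during the trial (to 12 weeks" and low potassium to "experiencing potassium levels lower than 3.5 mmol/L at any point during the trial (to 12 weeks". Section 15.2.4 repeats the 12-week limit for high potassium; its low-potassium sentence has no limit. The adverse-event endpoint in 10.2 is "experiencing an adverse event during the trial (to 12 weeks", and the outcome measure in 8.2 runs "between baseline and the end of the study (12 weeks". Section 11 calls week 12 the end of the trial and describes the later visit "as well as a further follow-up assessment at 14 weeks post baseline". The AE and SAE methods (15.2.3.1 and 15.2.3.2) and the AE and SAE outputs listed in section 16 state no window.

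**The concern.** The SAP narrows a protocol-defined endpoint, and its revision history neither lists nor explains the change. Followed literally, its endpoint definitions leave out the only scheduled visit after the planned stop of both drugs, although the data for that visit are collected. The adverse-event definition has the same cut-off, while the methods that implement it have none. Two analysts could therefore count different events and each claim to have followed the SAP.

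At stake is the completeness of the descriptive safety results. The trial closed early and hypothesis testing was removed (SAP 12.1 and 13.3), so readers will rely on counts, percentages and the odds ratios still shown in the SAP's Table 6. In a small sample, one omitted patient visibly changes a percentage.

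**Working it through.** The plan gives no figure for this point, so the check compares texts and counts days and visits.

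**1. What the protocol means by the study.** Section 11.6 separates a 12-week treatment period from 16 weeks in the study. The schedule agrees if the Day 98 visit is included: from Day −14 (earliest screening) to Day 98 is 98 + 14 = 112 days, and 112 / 7 = 16 weeks. Section 13.11 ends the trial after the last patient's last visit. A window covering the whole study therefore includes Day 98.

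**2. The windows side by side.**

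| Item | Protocol | SAP endpoint (8.2, 10.2) | SAP method (15.2) |
|---|---|---|---|
| High potassium | whole study | to week 12 | to week 12 |
| K <3.5 | whole study | to week 12 | no limit stated |
| Adverse events | no limit; assessed at Day 98 | to week 12 | no limit stated |
| SAEs | collected from consent to last visit | not defined separately | no limit stated |

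**3. Size of the excluded period.**
- Nominal: 98 − 84 = 14 days; 14 / 98 = 14.3%.
- With ±4 days at both visits: from (98 − 4) − (84 + 4) = 6 days to (98 + 4) − (84 − 4) = 22 days.
- Scheduled post-baseline potassium measurements: Days 7, 14, 28, 42, 56, 84 and 98, seven in all. The SAP counts six; one of seven (14.3%) is left out.

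**4. Whether another output catches a Day 98 value.** Change in potassium is computed only to week 12 (SAP 10.2 and 15.2.1). Protocol 17.6 does not expect potassium changes to be reported as adverse events unless they accompany an SAE or are events of special interest. Protocol 17.5 sets the special-interest thresholds at >6.5 and <3.5. Hence:
- Day 98 K >6.5 or <3.5: outside the endpoint counts in 8.2 and 10.2, but reportable as an adverse event and possibly shown in the AE tables.
- Day 98 K >6 and ≤6.5 with no SAE: in no specified endpoint, and normally not in the AE tables either.

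**5. Illustrative count.** The documents give no event rate for Days 84 to 98. Assume that a proportion p of patients have their first qualifying event in that period, with the planned 58 per arm. Expected uncounted patients per arm = 58p; probability of at least one = 1 − (1 − p)^58.

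| p (assumed) | Expected uncounted per arm | P(at least one) |
|---|---|---|
| 1% | 0.58 | 0.442 |
| 3% | 1.74 | 0.829 |
| 5% | 2.9 | 0.949 |
| 10% | 5.8 | 0.998 |

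The sample actually obtained is smaller and is not stated, so these counts are upper illustrations for each p.

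**The case against.** The strongest defence is that an on-treatment window suits the question. Protocol 11.5 frames the potassium endpoints as effects of RASi optimisation enabled by SZC, and that exposure ends by plan at Day 84. The protocol also uses its terms loosely: uACR and pro BNP are set at the end of the study in 11.4, yet are scheduled after baseline only at Visit 7, and 11.5 calls that point the end of treatment. The SAP's label for week 12 fits that usage. This supports keeping a 12-week comparison. It does not support dropping Day 98 without a stated reason, given 11.6 and 13.11.

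Three stronger readings are tempting and do not hold:
- *That the cut-off favours SZC.* Irbesartan stops at the same visit as the binder, and patients return to their earlier ACE/ARB, which by eligibility was at most half the maximum dose or none. The two withdrawals could offset each other, and the documents give no rate or net direction.
- *That a late SAE would go unreported.* The AE and SAE methods have no cut-off, so a late SAE could still be listed and a late special-interest potassium value still tabulated. What is lost is its place in the endpoint proportion.
- *That all off-treatment observation is discarded.* Patients whose IMP is withheld early continue visits (13.9 and 13.10), so some off-IMP data fall before Day 84. Day 98 is only the sole scheduled visit after the planned stop.

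The conflict on adverse events also does not rest on the protocol's whole-study phrase, which applies to potassium alone. It rests on the uncapped AE endpoint, the Visit 8 assessment and SAE collection to the last visit.

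**Conclusion.** The SAP's endpoint definitions do not match the protocol's potassium endpoints, and they cap the adverse-event endpoint where the protocol does not. The AE cap also conflicts with the SAP's own uncapped methods. The gap is 14 of 98 nominal days (6 to 22 with visit windows) and one of seven scheduled post-baseline potassium measurements. The clearest loss is a Day 98 potassium above 6 and not above 6.5.

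The number of patients affected cannot be derived from the documents, and the direction of any effect on the SZC–placebo comparison is unknown. The conclusion rests on reading the protocol's study period as including Day 98, which its 16-week duration and end-of-trial definition support. One caveat is that SAP section 6 says it was written from protocol version 1.0, which is not available here; the comparison is with version 1.1. The SAP should be corrected. The finding does not show that the safety conclusions are biased.

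**What to change.** In SAP 8.2, 10.2, 15.2.3 and 15.2.4, set one window for adverse events and for potassium >6, >6.5 and <3.5: baseline to the last study visit (Day 98), including unscheduled samples. Report two periods separately:
- on-treatment, to the patient's actual Visit 7;
- post-treatment, from Visit 7 to Day 98, with the number of patients who have a sample in that period as the potassium denominator.

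Keep the 12-week between-group comparison as it stands. Separate columns stop the effects of the double withdrawal from being mixed into it. A footnote should identify patients who stopped IMP before Visit 7. Record the change and its reason in the revision history.

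The cost is SAP wording and one extra column in the safety tables. The schedule already provides for the data, and the planned sample size (98, or 116 with drop-out) does not depend on this window. Whether to list SAEs from consent is a separate matter: the safety set is limited to dosed patients, and an event before randomisation belongs to no arm.

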11. ASSESSMENT OF OBJECTIVES

Upon successful screening and meeting all eligibility criteria for inclusion into the trial, as specified in the protocol, consenting patients will be randomised to either receive Szc therapy or placebo. Patients will receive trial treatment in accordance with the protocolised management of irbesartan and Szc/placebo, as described in Figure 2.

[figure not shown]
After screening and baseline, patients will be assessed at 1 week, 2 weeks, 4 weeks, 6 weeks, 8 weeks and 12 weeks (end of the trial), as well as a further follow-up assessment at 14 weeks post baseline. The assessment schedule is shown in the Table 1.

Table 1: Schedule of assessment

Schedule of visits	Screening	Visit 1	Visit 2	Visit 3	Visit 4	Visit 5	Visit 6	Visit 7	Follow-up visit	Unscheduled	Early termination visit
Day/Month	Day -14 to -7	Day 0	Day 7 (+/- 2)	Day 14 (+/- 4)	Day 28 (+/- 4)	Day 42 (+/- 4)	Day 56 (+/- 4)	Day 84 (+/- 4)	Day 98 (+/- 4)		
Informed Consent	X										
Eligibility criteria	X	X									
Demographic data	X										
Medical history	X										
Pregnancy test if WOCBP	X										
Concomitant medication	X	X	X	X	X	X	X	X	X	if needed	X
Randomisation		X									
Stop background antihypertensives	X										
First IMP dose at site		X									
Drug accountability (IRB and SZC)			X	X	X	X	X	X		If needed	
IMP and NIMP drug dispense		X			X		X			If needed	
Physical examination	X	X	X	X	X	X	X	X	X	If needed	X
Vital signs	X	X	X	X	X	X	X	X	X	If needed	X
FBC		X						X		If needed	
U+E	X	X	X	X	X	X	X	X	X	If needed	X
Pro NT BNP		X						X			
Optional POC potassium		X	X	X	X	X	X	X			
ECG	X	X	X	X	X	X	X	X	X	If needed	X
Urine collection (uACR)		X						X		If needed	

AE assessment		X	X	X	X	X	X	X	X	X	X
Uptitration of RASI			X	X	X	X	X			If needed	
RASI dose back to baseline								X			X

Figure 2: Protocolised management of irbesartan and SZC/placebo

12. POWER CALCULATION

From published data, reduction in serum potassium with SZC is between 0.7-1mmol/l. From this data we hypothesise that 30% of patients on placebo will get to maximum dose of irbesartan (300 mg) and double the number of patients (60%) on irbesartan will get to maximum dose of irbesartan by the end of the study (12 weeks). Under these assumptions, the sample size calculation using a 2-sided Chi-square test at the 5% level of significance, with 80% power to detect the assumed difference, led to a total sample size of 98 patients (49 in each trial group).

We envisage reasons for possible patient drop-out from the trial to be either a result of a decline in eGFR or hypotension. Assuming a 15% drop-out rate, we inflate the sample size to 116 patients (58 in each trial group).

12.1. Obtained sample size

Due to early study closure the calculated sample size has not been reached. Data analysis will focus on making the best use of the obtained sample.

13. GENERAL ANALYSIS DEFINITIONS

13.1. Analysis populations

13.1.1. Primary and exploratory analyses

All analyses will be conducted on an intention-to-treat (ITT) population, based on the group to which they were randomised, regardless of their compliance or which treatment they received. Those subjects who are removed from the trial early due to having been found to not meet entry criteria for the trial will not be included in analyses.

The main approach to the analysis of trial endpoints will include all subjects that have data on the endpoint being analysed, i.e., complete case analysis for each endpoint.

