##### Analysis of the primary endpoint

The primary endpoint will be analysed using the ITT principle, i.e. all randomized patients will be included. The analysis itself will be performed by means of a 2-sided chi-squared test, with a p-value < 0.05 indicating that the null hypothesis of no difference can be rejected. Patients with missing primary endpoint will be excluded from the analysis. However, the impact of such an exclusion on the results will be evaluated by considering different hypothetical scenarios where e.g. all patients in the SZC group for which failure or success could not be determined are assumed to be “failures”, while all such patients in the placebo group are assumed to be “successes”.

Sub-group analyses for primary endpoint per e.g. S-K at screening might be performed in order to explore consistency of effect.

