## 19.11 Procedure(s) to account for missing or spurious data

This is a short study; therefore, we do not expect dropout rates to be significant. In the consent form we will gain consent to access their GP records to allow us to follow the patients if they do drop out for outcome events.

We plan to minimise dropout rates as we are experienced at delivering clinical trials, we have a good patient network and will not enrol patients who we feel are unlikely to complete the study. If there is missing outcome data, sensitivity analysis will be undertaken to examine the impact..

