13.2. Missing data

All endpoints will be analyzed on a complete case basis, on all subjects with available data for the endpoint being analysed. The level of missing data (number and percentage) will be presented for each endpoint by the trial group.

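### SAP v1.1 omits the missing-data scenarios that protocol 19.3 requires for the primary endpoint, excludes randomised patients found ineligible, and does not classify early exits

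*SAP*

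**What the plan says.** **Protocol.** Section 19.3 sets three rules for the primary endpoint:
- Population: "The primary endpoint will be analysed using the ITT principle, i.e. all randomized patients will be included".
- Main rule for missing data: "Patients with missing primary endpoint will be excluded from the analysis".
- Check on that rule: "the impact of such an exclusion on the results will be evaluated by considering different hypothetical scenarios". The example given counts undetermined SZC patients as failures and undetermined placebo patients as successes.

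Section 19.11 adds: "If there is missing outcome data, sensitivity analysis will be undertaken to examine the impact". It also plans consent to "access their GP records to allow us to follow the patients if they do drop out for outcome events".

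**SAP v1.1.** Section 13.1.1 names an ITT population, grouped as randomised whatever the compliance, and then makes complete case the main approach: "The main approach to the analysis of trial endpoints will include all subjects that have data on the endpoint being analysed". Section 13.2 repeats this: "All endpoints will be analyzed on a complete case basis, on all subjects with available data for the endpoint being analysed". It adds the number and percentage missing by group. Section 13.1.1 also says that subjects "removed from the trial early due to having been found to not meet entry criteria for the trial will not be included in analyses". Section 15.1 reports the number and percentage on 300 mg in each group and the number with no data. Table 2 in section 16 adds an odds ratio with a 95% confidence interval. None of these sections contains a scenario or sensitivity analysis for the primary endpoint.

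**Early exits.** Protocol 19.1 gives eGFR change and hypotension as the reasons why patients on the IMP would not reach 300 mg. SAP 12 gives the same two as the expected reasons for drop-out from the trial.

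**The concern.** The SAP falls short of the protocol in two places: the ineligibility exclusion and the absent scenarios. Separately, it leaves one classification open. A patient who leaves because of falling eGFR or low blood pressure could be entered as not on 300 mg or as missing, and the two documents point in different directions.

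If such exits are treated as missing, the patients dropped are those whom protocol 19.1 expects not to reach 300 mg. The reported success percentages are then too high, and the difference and odds ratio may shift. The protocol's scenarios would show how far, and the SAP has no substitute for them. An unwritten rule also means that the choice is made when the data are already in hand.

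**Working it through.** **1. The passages side by side**

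| Item | Protocol 19.3 / 19.11 | SAP v1.1 |
|---|---|---|
| Population | All randomised | Randomised, less those removed early as ineligible |
| Missing primary endpoint | Excluded | Excluded |
| Hypothetical scenarios | Required, with an example | None |
| Sensitivity analysis | Promised if outcome data are missing | None |
| Early exit for eGFR or blood pressure | Not classified | Not classified |

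Row 2 agrees. Rows 1, 3 and 4 are the departures. Row 5 is a gap in both documents.

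**2. The plan's own figure**

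Inputs (protocol 19.1, SAP 12): 60% v 30%, two-sided 5%, 80% power, 15% drop-out.

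- Uncorrected n per arm = [1.960 × √(2 × 0.45 × 0.55) + 0.842 × √(0.30 × 0.70 + 0.60 × 0.40)]² / 0.30² = 41.97.
- With continuity correction: (41.97 / 4) × [1 + √(1 + 4 / (41.97 × 0.30))]² = 48.4, so 49 per arm and 98 in total.
- Inflation: 98 / 0.85 = 115.3, so 116, or 58 per arm.

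Both stated totals reproduce. The inflation treats 98 as completers, so the first illustration applies 60% and 30% to completers.

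**3. Size on that reading** (15% drop-out in each arm)

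| Handling of drop-outs | SZC | Placebo | Difference | Odds ratio |
|---|---|---|---|---|
| Complete case | 60.0% | 30.0% | 30.0 points | 3.50 |
| All count as failures | 0.60 × 0.85 = 51.0% | 0.30 × 0.85 = 25.5% | 25.5 points | 3.04 |
| Protocol scenario, all undetermined | 51.0% | 25.5% + 15% = 40.5% | 10.5 points | 1.53 |

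In whole patients (58 per arm, 9 exits each, 29/49 v 15/49 observed), the three rows give 28.6, 24.1 and 8.6 points, with odds ratios 3.29, 2.87 and 1.42.

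**4. Direction**

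Same reading, all drop-outs failures, unequal drop-out (assumed). Complete case stays at 30.0 points and 3.50.

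- 20% SZC, 10% placebo: 48.0% v 27.0%, 21.0 points, odds ratio 2.50. Complete case overstates.
- 5% SZC, 25% placebo: 57.0% v 22.5%, 34.5 points, odds ratio 4.57. Complete case understates.

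The other reading follows protocol 19.1 and puts these exits inside the shortfall, so that about 60% and 30% apply to everyone randomised: 35/58 v 17/58, 31.0 points, odds ratio 3.67. Complete case then gives:

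- 9 and 9 exits dropped: 35/49 v 17/49, 36.7 points, odds ratio 4.71.
- 3 SZC and 14 placebo dropped: 35/55 v 17/44, 25.0 points, odds ratio 2.78.
- 14 SZC and 3 placebo dropped: 35/44 v 17/55, 48.6 points, odds ratio 8.69.

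On either reading the bias can go both ways.

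**5. Small samples**

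The obtained number is not stated. With an assumed 5, 10 or 20 per arm and 1, 2 or 3 missing per arm, complete-case differences of 25.0, 37.5 and 29.4 points become 0, 10 and 10 points in the protocol's scenario.

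**The case against.** **The harm is small.** This stands. SAP 13.3 drops hypothesis testing. Missing counts by group (13.2), withdrawal reasons and a flow diagram (14), and success counts (15.1) are all reported, so a reader could largely work out the scenario by hand. Patients taken off the IMP are meant to continue visits, so their dose is recorded. Routine data (protocol 13.9) and GP records may fill some gaps. Protocol 19.11 expects little drop-out, and 15% is only a planning allowance. Even so, reporting counts is not the evaluation of impact that 19.3 calls for, and Table 2 still presents an odds ratio with an interval.

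**With so few patients the bounds say little.** This is partly right. A wide range is nonetheless the honest description of what the data can show, and the scenario needs only counts, so the reason given for dropping tests does not extend to it.

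**Stronger readings that a reader might infer, and why they are not supported:**
- *That an ITT label on a complete-case analysis contradicts the protocol.* Protocol 19.3 makes the same pairing, and SAP 13.1.1 says openly what it does.
- *That the scenarios were removed in v1.1.* The revision log does not mention them, and SAP v1.0 is not supplied.
- *That every early exit should be a failure in the main analysis.* Protocol 19.3 excludes missing endpoints from the main analysis. A patient on 300 mg who leaves for an unrelated reason is not an observed failure.
- *That complete case flatters SZC unless placebo drop-out is at least double.* This holds only for the risk difference, with 60%/30% in completers and every drop-out a failure. Table 2's effect measure is the odds ratio. With 10% SZC drop-out, that is already understated once placebo drop-out exceeds about 16.3%.

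**Conclusion.** The point holds as a minor one. SAP v1.1 departs from protocol 19.3 by excluding randomised patients removed as ineligible, and from 19.3 and 19.11 by containing no scenario or sensitivity analysis for the primary endpoint. It also leaves exits for eGFR decline or hypotension unclassified.

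On planning figures, the way drop-outs are handled moves the difference from 30.0 points to 25.5 or 10.5, and the odds ratio from 3.50 to 3.04 or 1.53. These figures assume 60%/30% in completers and 15% drop-out in each arm. They illustrate sensitivity and do not estimate this trial's bias: the obtained sample and its missing data are not given, and the direction depends on how drop-out splits between arms and on whether the 60%/30% already include such exits.

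**What to change.** 1. **SAP 13.1.1:** delete the ineligibility exclusion, so that all randomised patients are accounted for in their randomised group. Those without a week-12 dose count as undetermined.
2. **SAP 13.2, 15.1 and Table 2:** keep the protocol's main row, with missing endpoints excluded. Add a descriptive row over all randomised patients that counts undetermined SZC patients as failures and undetermined placebo patients as successes.
3. **Table 2:** add a sensitivity row, separate from the main row, that counts as not on 300 mg those early exits with a recorded eGFR or blood-pressure reason. Patients who give no reason, as protocol 13.3.2 allows, stay undetermined.
4. **SAP 15.1:** state that week-12 status is the irbesartan dose held before the Visit 7 return to the original ACE inhibitor or ARB. Returning RASI to baseline cannot itself mark a failure: protocol 13.8.3 does it for all patients at Visit 7, and SAP Table 1 also marks it at early termination. Have exits classified blind to allocation.

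The cost is SAP wording, two descriptive rows, and sorting exits by the reason already recorded on the study termination form (protocol 13.9). No new data are needed. Deleting the exclusion changes the main row little, because removed patients without a week-12 dose stay out of it; the effect is mainly in the scenario row.
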